8.1.1.1 Interaction of eltrombopag with other medicinal products and food

Effects of eltrombopag on other medicinal products

HMG CoA reductase inhibitors

In vitro studies demonstrated that eltrombopag is not a substrate for the organic anion transporter polypeptide, OATP1B1, but is an inhibitor of this transporter. *In vitro* studies also demonstrated that eltrombopag is a breast cancer resistance protein (BCRP) substrate and inhibitor. Administration of eltrombopag 75 mg once daily for 5 days with a single 10 mg dose of the OATP1B1 and BCRP substrate rosuvastatin to 39 healthy adult subjects increased plasma rosuvastatin C_{max} 103 % (90 % CI: 82 %, 126 %) and $AUC_{0-\infty}$ 55 % (90 % CI: 42 %, 69 %). Interactions are also expected with other HMG-CoA reductase inhibitors, including pravastatin, simvastatin and lovastatin, however, clinically significant interactions are not expected between eltrombopag and atorvastatin or fluvastatin. When co-administered with eltrombopag, a reduced dose of statins should be considered and careful monitoring for statin side effects should be undertaken.

OATP1B1 and BCRP substrates

Concomitant administration of eltrombopag and OATP1B1 (e.g. methotrexate) and BCRP (e.g. topotecan and methotrexate) substrates should be undertaken with caution.

Cytochrome P450 substrates

In studies utilizing human liver microsomes, eltrombopag (up to 100 μ M) showed no *in vitro* inhibition of the CYP450 enzymes 1A2, 2A6, 2C19, 2D6, 2E1, 3A4/5, and 4A9/11 and was an inhibitor of CYP2C8 and CYP2C9 as measured using paclitaxel and diclofenac as the probe substrates. Administration of eltrombopag 75 mg once daily for 7 days to 24 healthy male subjects did not inhibit or induce the metabolism of probe substrates for 1A2 (caffeine), 2C19 (omeprazole), 2C9 (flurbiprofen), or 3A4 (midazolam) in humans. No clinically significant interactions are expected when eltrombopag and CYP450 substrates are co-administered.

Effects of other medicinal products on eltrombopag

Polyvalent cations (Chelation)

Eltrombopag chelates with polyvalent cations such as iron, calcium, magnesium, aluminium, selenium and zinc. Administration of a single dose of eltrombopag 75 mg with a polyvalent cation-containing antacid (1524 mg aluminium hydroxide and 1425 mg magnesium carbonate) decreased plasma eltrombopag $AUC_{0-\infty}$ by 70 % (90 % CI: 64 %, 76 %) and C_{max} by 70 % (90 % CI: 62 %, 76 %). Antacids, dairy products and other products containing polyvalent cations, such as mineral supplements, must be administered at least four hours apart from eltrombopag dosing to avoid significant reduction in eltrombopag absorption due to chelation.

Food interaction

Administration of a single 50 mg-dose of eltrombopag with a standard high-calorie, high-fat breakfast that included dairy products reduced plasma eltrombopag $AUC_{0-\infty}$ by 59 % (90 % CI: 54 %, 64 %) and C_{max} by 65 % (90 % CI: 59 %, 70 %). Food low in calcium [< 50 mg calcium] including fruit, lean ham, beef and unfortified (no added calcium, magnesium, iron) fruit juice, unfortified soy milk, and unfortified grain did not significantly impact plasma

eltrombopag exposure, regardless of calorie and fat content (see section on eltrombopag administration).

Lopinavir/ritonavir

Co-administration of eltrombopag with lopinavir/ritonavir (LPV/RTV) may cause a decrease in the concentration of eltrombopag.⁷ However, no patient in this study is expected to receive concomitant lopinavir/ritonavir.

8.1.1.2 Continuation of eltrombopag treatment based on 3 month hematological response

The extension of treatment with eltrombopag up to 6 months is based on hematological response at 3 months.

- Eltrombopag will be discontinued in all patients achieving complete response at 3 months
 - For these patients, re-introduction of eltrombopag is allowed in case of relapse, as described below;
- Eltrombopag will be continued up to 6 months, at the same dose, in:
 - Patients achieving partial response at 3 months;
 - Patients with no hematological response at 3 months.

8.1.1.3 Re-introduction of eltrombopag

For patients achieving hematological response (either complete or partial) who have discontinued eltrombopag, the agent can be re-introduced in case of relapse (see paragraph 9.3) or lack of robustness of hematological response occurring **within 6 months from discontinuation of eltrombopag**.

The following patients are eligible for re-introduction of eltrombopag within this study:

- Patients in CR at 3 months, who have discontinued eltrombopag as per protocol, with subsequent relapse (defined as no longer meeting the criteria of CR);
- Patients who have discontinued eltrombopag at 6 months as per protocol, and:
 - Were in CR at 6 months, with subsequent relapse (defined as no longer meeting the criteria of CR);
 - Were in PR at 6 months, with subsequent relapse (defined as no longer meeting the criteria of PR);
 - Were in PR at 6 months, with subsequent lack of robustness of their PR, defined as follows (any of these):
 - Drop in Hb >2 gr/dL (with Hb <10 gr/dL);
 - Drop >50% in ANC (with ANC <1,000/ μ L);
 - Drop >50% in Plt count (with Plt <50,000/ μ L).

In all these circumstances the second course of eltrombopag treatment will be started at the same dose of 150 mg/day, and will be continued for 3 months in case of complete response at

⁷ A study in 40 healthy volunteers showed that the co-administration of single dose eltrombopag 100 mg with repeat dose LPV/RTV 400 /100 mg twice daily resulted in a reduction in eltrombopag plasma AUC_(0-∞) by 17 % (90 % CI: 6.6 %, 26.6 %). Therefore, caution should be used when co-administration of eltrombopag with LPV/RTV takes place. Platelet count should be closely monitored in order to ensure appropriate medical management of the dose of eltrombopag when lopinavir/ritonavir therapy is initiated or discontinued.

3 months from re-introduction, or up to 6 months. After these additional 6 months of treatment, eltrombopag may be continued outside the protocol by the physician in charge of the patients but won't be furnished anymore by Novartis. Patients with transient falls in blood counts secondary to infectious complication or any other medical conditions do not qualify for re-introduction of eltrombopag. Similarly, patients with late relapses (>6 months from eltrombopag discontinuation), at time of CsA tapering or discontinuation, do not qualify for re-introduction of eltrombopag within this study.

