8.11.1 Open-label eltrombopag treatment

The following patients will be eligible for open-label eltrombopag treatment:

- Patients randomized in the control arm (ATGAM + CsA without eltrombopag) who:
 - Show no hematological response at 6 months;
 - Do not demonstrate any clonal evolution at 6 months (as confirmed by bone marrow karyotyping);

(See section 12 for related methodological issues)

All these patients are eligible to receive a course of eltrombopag; at judge of the investigator, eltrombopag will be offered as either:

- Single agent treatment;
- Eltrombopag associated with second course of immunosuppression (without any restriction concerning the anti-lymphocyte agent).

Eltrombopag treatment will be started at the same dose of 150 mg/day, and will be continued for 3 months in case of complete response at 3 months from re-introduction, or up to 6 months. After these 6 months of treatment, eltrombopag will be discontinued in any case independently from hematological response; the patients will continue the follow up, as prescribed per protocol (see paragraph 7.2).

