9.1.1 Complete response (CR)

Patients will be considered as complete responders (CR) if achieving all the following:

- Following peripheral blood counts:
 - Hemoglobin >10 gr/dL
 - Absolute neutrophils >1.0 x 10⁹/L
 - Platelets >100 x 10⁹/L
- No evidence of clonal evolution (by marrow cytogenetic and flow cytometry, see below 9.5)

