9.1.2 Partial response (PR)

Patients will be considered as partial responders (PR) if achieving **all** the following:

- No longer meet criteria for diagnosis of SAA
- Transfusion independence (defined as no need of any PRBC or platelet transfusion)
- Peripheral blood counts:
 - Hemoglobin >8 gr/dL
 - Absolute neutrophils >0.5 x 10⁹/L
 - Platelets >20 x 10⁹/L

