9.3 Definition clinical relapse (Cl-Rel)

Clinical relapse is considered as the occurrence of any of the following event in a patient who had showed a hematological response (CR or PR):

- meeting again the criteria for SAA
- requirement of transfusion support (if not due to independent medical conditions)
- decrease in any of the peripheral blood counts as follows
 - Decrease to less than 50% of the medium sustained count during remission if:
 - absolute neutrophils $< 1.0 \times 10^9/L$
 - platelets $< 50 \times 10^9/L$

Or

- In any case if:
 - absolute neutrophils $< 0.5 \times 10^9/L$
 - platelets $< 20 \times 10^9/L$

To qualify a relapse peripheral blood count decrease has to be

- not due to any independent concomitant medical condition
- demonstrated for a minimum of 3 determination over a period of 2 weeks
- not responding to re-introduction of low dose cyclosporin A

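### Section 8.1.1.3 does not exclude patients with clonal evolution from restarting eltrombopag, although 8.11.1 excludes them from control-arm rescue with the same drug and dose

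*Protocol*

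**What the plan says.** Under 8.1.1.2, eltrombopag stops at month 3 in complete responders and continues up to month 6 in everyone else.

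Section 8.1.1.3 then governs restarting:

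- Its lead-in says that "the agent can be re-introduced in case of relapse (see paragraph 9.3") or for lack of robustness, within 6 months of stopping.
- Its list of eligible patients covers those in CR at month 3 or month 6 "with subsequent relapse (defined as no longer meeting the criteria of CR").
- It also covers those in PR at month 6 "with subsequent relapse (defined as no longer meeting the criteria of PR") or with specified falls in haemoglobin, ANC or platelets.
- The second course, at 150 mg/day, "will be continued for 3 months in case of complete response at" the 3-month point after restarting, and otherwise for up to 6 months.
- Two groups are ruled out: transient count falls from infection or other medical conditions, and relapses later than 6 months after stopping.

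The response definitions differ on clonal status. CR (9.1.1) requires "No evidence of clonal evolution (by marrow cytogenetic and flow cytometry, see below 9.5"). PR (9.1.2) begins with "No longer meet criteria for diagnosis of SAA" and adds transfusion independence and count thresholds. It says nothing about clonal evolution.

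Section 8.11.1 offers the same drug at the same dose to control-arm non-responders at month 6, on the condition that they "Do not demonstrate any clonal evolution at 6 months (as confirmed by bone marrow karyotyping").

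**The concern.** CR is defined partly by the absence of clonal evolution, and loss of CR is a route to more drug. New clonal evolution can therefore by itself meet the listed condition for restarting. The partial-response route never asks about clonal status.

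What is at stake is patient safety. Section 2.4.1 accepts that the drug might stimulate stem cells carrying malignant or pre-malignant mutations, 8.3.1 records a concern about progression of MDS, and Appendix 5 singles out clonal evolution for special attention. Section 8.11.1 acts on this hazard with an eligibility condition. Section 8.1.1.3, which covers experimental-arm patients receiving a further course, does not, and no reason is given for the difference.

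**Working it through.** No formula applies to the main point, so the check sets the sections side by side.

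**1. Who may restart, and when.** Month-3 stoppers have a window from month 3 to 3 + 6 = 9, and month-6 stoppers from month 6 to 6 + 6 = 12. On the Appendix 2 schedule, the marrow falling after the stop is at month 6 for the first group and at month 12 for the second.

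**2. Does clonal evolution block any route?**

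| Patient | Listed condition in 8.1.1.3 | Relapse under 9.3 | Clonal bar |
|---|---|---|---|
| Former CR, counts preserved, new clonal evolution | Met (CR lost under 9.1.1) | No | None |
| Former CR, new clonal evolution and falling counts | Met | Depends on depth of fall | None |
| Month-6 PR with clonal evolution, PR later lost or not robust | Met | Depends on depth of fall | None |
| Control-arm non-responder with clonal evolution (8.11.1) | Not applicable | Not applicable | Excluded |

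**3. Can clonal evolution be diagnosed inside the window?** Section 9.5 implies that an abnormality listed in Appendix 1 can by itself qualify as MDS. Appendix 1 has 8 unbalanced + 6 balanced = 14 entries, plus complex karyotypes involving one of them. Its caption refers to persistent cytopenia, so this implication is weaker when counts are preserved. An unlisted abnormality needs two marrows at least 3 months apart. On scheduled marrows, a month-3 stopper meets that inside the window only if the month-3 and month-6 samples are both positive.

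**4. How far apart are the two relapse wordings?** Section 9.3 needs SAA criteria, transfusion need or a count fall. The count fall is either "Decrease to less than 50% of the medium sustained count during remission if" ANC is below 1.0 or platelets below 50 × 10⁹/L, or in any case ANC below 0.5 or platelets below 20. There is no haemoglobin count limb. Illustrative patients:

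- CR, platelets 150 to 95: CR lost. 95/150 = 63% and above 50, so no 9.3 relapse.
- CR, ANC 1.6 to 0.9: CR lost. 0.9/1.6 = 56% and above 0.5, so no 9.3 relapse.
- CR, Hb 13 to 9.5 g/dL, untransfused: CR lost, no 9.3 relapse.
- PR, platelets 60 to 28: 28/60 = 47% and below 50, so a 9.3 relapse if confirmed. PR still holds by count (above 20), so the list calls this lack of robustness.

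The wordings differ in both directions. Section 9.3 also requires at least 3 determinations over 2 weeks, no independent medical cause, and no response to re-introduced low-dose cyclosporin. The list repeats none of these, apart from its exclusion of transient falls.

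**The case against.** **The lead-in blocks the preserved-counts case.** It ties restarting to 9.3, and clonal evolution alone is not a 9.3 relapse. This stands as a reason to call the eligibility literal rather than intended. It does not help once counts fall, and it does not help the PR route, because 9.3 has no clonal exclusion either. Its exception for an independent concomitant condition does not name clonal evolution.

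**The two definitions are an editorial slip.** This largely stands. Section 8.1.1.2 points to the description that follows, and the bracketed definitions are specific to each route, so the list naturally governs. A reader might infer a serious contradiction, but the text supports only a clarification.

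**Other safeguards exist.** Section 6.3 tells investigators to withdraw patients from treatment when continuing is not in their interest. Section 8.3.1 advises stopping for new morphological abnormalities or cytopenias. The IDMC reviews safety data every 6 months. The transient-falls sentence excludes some patients. These make harm less likely, but none is an eligibility rule for restarting. The transient-falls sentence does not name clonal evolution, whose falls need not be transient. The 8.3.1 advice concerns stopping, and cytopenia is itself a trigger for restarting. Under 10.2.3, clonal evolution does not need immediate SAE reporting, so IDMC review may come after the decision.

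**Three stronger readings are tempting but unsupported.**

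- That 8.1.1.3 contradicts 8.11.1: the two sections cover different patients, so this is an uneven safeguard and not a contradiction.
- That clonal evolution forces a full 6-month second course because CR cannot be regained: 9.1.1 asks for no evidence of clonal evolution, and nothing says a later negative marrow could not satisfy it. With 6 months taken as 365/2, about 183 days, total exposure of 75 + 183 = 258 days or 166 + 183 = 349 days is simply what any re-introduced patient may receive. It lies within the 12-month maximum of 7.2.3 and does not measure excess harm.
- That endpoint comparisons are biased, or that none is: the month-3 primary endpoint precedes restarting and is unaffected. Re-treatment at mere loss of CR, in one arm only, could delay a 9.3 relapse, but the protocol gives no basis for sizing this.

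**Conclusion.** The gap is real. No route to restarting eltrombopag in 8.1.1.3 excludes clonal evolution, and the CR route literally turns it into a qualifying event, while 8.11.1 excludes it for the same drug and dose. The number of patients is probably small and cannot be derived, because the protocol gives neither the rate of clonal evolution in the windows nor the rate of restarting. The text permits further drug and does not require it, so harm also depends on an investigator choosing to restart with the result known.

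The conclusion rests on reading the eligibility list as the operative rule, and for the preserved-counts case on taking its bracketed definition at its word. The PR route and the falling-counts cases do not need that second assumption. A short amendment is justified on patient-safety grounds. The mismatch between the lead-in and the list is secondary.

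**What to change.** Add to 8.1.1.3, for all routes: *Patients in whom clonal evolution (9.5) has been diagnosed since randomisation, on the marrow results available at re-introduction, are not eligible; del(20q), +8 or -Y present at baseline do not by themselves count.* The carve-out matches exclusion criterion 3 in 6.2.

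As a secondary clarification, state that the list defines the trigger and that it is count-based. For CR patients this means loss of a 9.1.1 threshold (Hb >10 g/dL, ANC >1.0 × 10⁹/L or platelets >100 × 10⁹/L). For PR patients it means loss of PR or the listed lack of robustness. Keep from 9.3 the requirements of at least 3 determinations over 2 weeks and no independent medical cause. Otherwise a single platelet count of 99 could open up to 6 more months of drug. The low-dose cyclosporin condition need not be carried over: cyclosporin continues for at least 12 months (8.1.3, 8.12), so it can rarely be tested in windows that close at month 9 or 12.

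The cost is a few sentences, a line on the form used to request a second course, and the approvals in 14.6. No marrow is added, so the latest scheduled result may be up to 3 months old in month-3 stoppers and up to 6 months old in month-6 stoppers. A few patients lose an optional treatment. An unlisted abnormality not yet confirmed on a second marrow is still not barred.

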8.1.2 Horse ATG (ATGAM)

Patients will receive horse-ATG (ATGAM) for 4 consecutive days (days 1-4), at the dose of 40 mg/kg/day, as a i.v. infusion lasting 12-18 hours. As prevention of ATGAM-related side effects, including serum sickness, corticosteroids will be administered at the dose of 1 mg/kg/day (either intravenously or orally) for at least 7 days (see below) and then tapered and stopped within 2-3 weeks post treatment. A pre-medication with paracetamol (e.g. 1000 mg) and/or anti-histaminic medications (e.g. clorpheniramine 10 mg) are allowed as well.

For obese patients ATGAM will be dosed according to average between 1.3 x IBW and actual weight.

Obesity is defined as any weight above 1.3 x IBW (BMI will not be used).

IBW calculation can be found on: <http://www.manuelsweb.com/IBW.htm>

IBW

Estimated ideal body weight in (kg)

Males: $IBW = 50 \text{ kg} + 2.3 \text{ kg for each inch over 5 feet.}$

Females: $IBW = 45.5 \text{ kg} + 2.3 \text{ kg for each inch over 5 feet}$

In case the final weight used for dosing is > 100 kg, the infusion volume has to be increased > 1 l.

8.1.2.1 Interaction of ATGAM with other medicinal products and food

Effects of ATGAM on other medicinal products

Dextrose injection

Dilution of ATGAM in dextrose injection, USP, is not recommended, as low salt concentrations may result in precipitation.

Highly acidic infusion solutions

The use of highly acidic infusion solutions is not recommended because of possible physical instability over time.

Effects of other medicinal products on ATGAM

Corticosteroids and other Immunosuppressants

When the dose of corticosteroids and other immunosuppressants is being reduced, some previously masked reactions to ATGAM may appear. Under these circumstances, observe patients especially carefully during therapy with ATGAM.

8.1.3 Cyclosporine A

Patients will receive oral cyclosporin starting on day 1 of treatment at the dose of 5 mg/kg orally, and then adjusted on blood levels (150-250 ng/mL using the monoclonal assay, 200-400 ng/mL using the polyclonal assay). Treatment will be continued for at least 12 months, and then slowly tapered according to clinical conditions (see below).

8.1.3.1 Interaction of Cyclosporine A with other medicinal products and food

Effects of Cyclosporine A on other medicinal products

Cyclosporine A is an inhibitor of CYP3A4 and of multiple drug efflux transporters and may increase plasma concentrations of co-medications that are substrates of CYP3A4, P-glycoprotein, or organic anion transporter proteins.

Cyclosporine A may reduce the clearance of:

Digoxin

Severe digitalis toxicity has been seen within days of starting cyclosporine A in several patients taking digoxin. If digoxin is used concurrently with cyclosporine A, serum digoxin concentrations should be monitored.

Colchicine

There are reports on the potential of cyclosporine A to enhance the toxic effects of colchicine such as myopathy and neuropathy, especially in patients with renal dysfunction. Concomitant administration of cyclosporine A and colchicine results in significant increases in colchicine plasma concentrations. If colchicine is used concurrently with cyclosporine A, a reduction in the dosage of colchicine is recommended.

HMG-CoA reductase inhibitors (statins)

Literature and postmarketing cases of myotoxicity, including muscle pain and weakness, myositis, and rhabdomyolysis, have been reported with concomitant administration of cyclosporine A with lovastatin, simvastatin, atorvastatin, pravastatin, and rarely, fluvastatin. When concurrently administered with cyclosporine A, the dosage of these statins should be reduced according to label recommendations. Statin therapy needs to be temporarily withheld or discontinued in patients with signs and symptoms of myopathy or those with risk factors predisposing to severe renal injury, including renal failure, secondary to rhabdomyolysis.

Repaglinide

Cyclosporine A may increase the plasma concentrations of repaglinide and thereby increase the risk of hypoglycemia. In 12 healthy male subjects who received two doses of 100 mg cyclosporine A capsule orally 12 hours apart with a single dose of 0.25 mg repaglinide tablet (one half of a 0.5 mg tablet) orally 13 hours after the cyclosporine A initial dose, the repaglinide mean C_{max} and AUC were increased 1.8 fold (range: 0.6 to 3.7 fold) and 2.4 fold (range 1.2 to 5.3 fold), respectively. Close monitoring of blood glucose level is advisable for a patient taking cyclosporine A and repaglinide concomitantly.

Ambrisentan

Co-administration of ambrisentan (5 mg daily) and cyclosporine A (100 to 150 mg twice daily initially, then dosing to achieve C_{min} 150 to 200 ng/mL) for 8 days in healthy subjects resulted mean increases in ambrisentan AUC and C_{max} of approximately 2-fold and 1.5-fold, respectively, compared to ambrisentan alone. When coadministering ambrisentan with

cyclosporine A, the ambrisentan dose should not be titrated to the recommended maximum daily dose.

Anthracycline antibiotics

High doses of cyclosporine A (e.g., at starting intravenous dose of 16 mg/kg/day) may increase the exposure to anthracycline antibiotics (e.g., doxorubicin, mitoxantrone, daunorubicin) in cancer patients.

Aliskiren

Cyclosporine A alters the pharmacokinetics of aliskiren, a substrate of P-glycoprotein and CYP3A4. In 14 healthy subjects who received concomitantly single doses of cyclosporine A (200 mg) and reduced dose aliskiren (75 mg), the mean C_{max} of aliskiren was increased by approximately 2.5-fold (90% CI: 1.96 to 3.17) and the mean AUC by approximately 4.3 fold (90% CI: 3.52 to 5.21), compared to when these subjects received aliskiren alone. The concomitant administration of aliskiren with cyclosporine A prolonged the median aliskiren elimination half-life (26 hours versus 43 to 45 hours) and the T_{max} (0.5 hours versus 1.5 to 2.0 hours). The mean AUC and C_{max} of cyclosporine A were comparable to reported literature values. Coadministration of cyclosporine A and aliskiren in these subjects also resulted in an increase in the number and/or intensity of adverse events, mainly headache, hot flush, nausea, vomiting, and somnolence. The coadministration of cyclosporine A with aliskiren is not recommended.

Bosentan

In healthy subjects, co-administration of bosentan and cyclosporine A resulted in time-dependent mean increases in dose-normalized bosentan trough concentrations (i.e., approximately 21-fold on day 1 and 2-fold on day 8 (steady state)) compared to when bosentan was given alone as a single dose on day 1. (See also Effect of Drugs and Other Agents on Cyclosporine A Pharmacokinetics and/or Safety) Co-administration of cyclosporine A with bosentan should be avoided.

Dabigatran

The effect of cyclosporine A on dabigatran concentrations had not been formally studied. Concomitant administration of dabigatran and cyclosporine A may result in increased plasma dabigatran concentrations due to the P-gp inhibitory activity of cyclosporine A. Coadministration of cyclosporine A with dabigatran should be avoided.

Potassium sparing diuretics

Cyclosporine A should not be used with potassium-sparing diuretics because hyperkalemia can occur. Caution is also required when cyclosporine A is co-administered with potassium-sparing drugs (e.g., angiotensin-converting enzyme inhibitors, angiotensin II receptor antagonists), potassium-containing drugs as well as in patients on a potassium-rich diet. Control of potassium levels in these situations is advisable.

Nonsteroidal Anti-inflammatory Drug (NSAID) Interactions

Clinical status and serum creatinine should be closely monitored when cyclosporine A is used with NSAIDs in rheumatoid arthritis patients. Pharmacodynamic interactions have been reported to occur between cyclosporine A and both naproxen and sulindac, in that concomitant use is associated with additive decreases in renal function, as determined by ^{99m}Tc-diethylenetriaminepentaacetic acid (DTPA) and (p-aminohippuric acid) PAH clearances. Although concomitant administration of diclofenac does not affect blood concentrations of cyclosporine A, it has been associated with approximate doubling of

diclofenac blood levels and occasional reports of reversible decreases in renal function. Consequently, the dose of diclofenac should be in the lower end of the therapeutic range.

Methotrexate Interaction

Preliminary data indicate that when methotrexate and cyclosporine A were coadministered to rheumatoid arthritis patients (N=20), methotrexate concentrations (AUCs) were increased approximately 30% and the concentrations (AUCs) of its metabolite, 7-hydroxy methotrexate, were decreased by approximately 80%. The clinical significance of this interaction is not known. Cyclosporine A concentrations do not appear to have been altered (N=6).

Sirolimus

Elevations in serum creatinine were observed in studies using sirolimus in combination with full-dose cyclosporine A. This effect is often reversible with cyclosporine A dose reduction. Simultaneous coadministration of cyclosporine A significantly increases blood levels of sirolimus. To minimize increases in sirolimus blood concentrations, it is recommended that sirolimus be given 4 hours after cyclosporine A administration.

Nifedipine

Frequent gingival hyperplasia when nifedipine is given concurrently with cyclosporine A has been reported. The concomitant use of nifedipine should be avoided in patients in whom gingival hyperplasia develops as a side effect of cyclosporine A.

Methylprednisolone

Convulsions when high dose methylprednisolone is given concomitantly with cyclosporine A have been reported.

Other Immunosuppressive Drugs and Agents

Psoriasis patients receiving other immunosuppressive agents or radiation therapy (including PUVA and UVB) should not receive concurrent cyclosporine because of the possibility of excessive immunosuppression.

Effects of other medicinal products on Cyclosporine A

Drugs That May Potentiate Renal Dysfunction

Concomitant use of nonsteroidal anti-inflammatory drugs with cyclosporine A, particularly in the setting of dehydration, may potentiate renal dysfunction. Caution should be exercised when using other drugs which are known to impair renal function.

Grapefruit juice

Grapefruit and grapefruit juice affect metabolism, increasing blood concentrations of cyclosporine A, thus should be avoided.

Bosentan

Co-administration of bosentan (250 to 1000 mg every 12 hours based on tolerability) and Cyclosporine A (300 mg every 12 hours for 2 days then dosing to achieve a C_{min} of 200 to 250 ng/mL) for 7 days in healthy subjects resulted in decreases in the cyclosporine A mean dose-normalized AUC, C_{max}, and trough concentration of approximately 50%, 30% and

60%, respectively, compared to when cyclosporine A was given alone. Co-administration of cyclosporine A with bosentan should be avoided.

Boceprevir

Co-administration of boceprevir (800 mg three times daily for 7 days) and cyclosporine A (100 mg single dose) in healthy subjects resulted in increases in the mean AUC and C_{max} of cyclosporine A approximately 2.7-fold and 2-fold, respectively, compared to when cyclosporine A was given alone.

Telaprevir

Co-administration of telaprevir (750 mg every 8 hours for 11 days) with cyclosporine A (10 mg on day 8) in healthy subjects resulted in increases in the mean dose-normalized AUC and C_{max} of cyclosporine A approximately 4.5-fold and 1.3-fold, respectively, compared to when cyclosporine A (100 mg single dose) was given alone.

St. John's Wort

There have been reports of a serious drug interaction between cyclosporine A and the herbal dietary supplement, St. John's Wort. This interaction has been reported to produce a marked reduction in the blood concentrations of cyclosporine A, resulting in sub therapeutic levels, rejection of transplanted organs, and graft loss.

Rifabutin

Rifabutin is known to increase the metabolism of other drugs metabolized by the cytochrome P-450 system. The interaction between rifabutin and cyclosporine A has not been studied. Care should be exercised when these two drugs are administered concomitantly.

